## 4.1.6 Packaging, labelling, and re-supply

The investigational medicinal products will be provided by BI or a designated CRO. They will be packaged and labelled in accordance with the principles of Good Manufacturing Practice (GMP). Re-supply to the sites will be managed via an which will also monitor expiry dates of supplies available at the sites.

The label will be prepared according to EU Regulation No. 536/2014, Annex 6, Section D. Omitting certain particulars with the following justifications:

- "Investigator" was omitted from the label because patient cards are used.
- Additionally, each kit assigned to a patient will be registered as such in the IXRS. "Visit number" is omitted from the label as each kit assigned to a participant has a kit number and it be registered in the

Should local regulations outside the EU require these particulars, they will be added to the country-specific label text.

For the description of the label, refer to the ISF.

Clinical Trial Protocol

Page 67 of 177

Proprietary confidential information © 2023 Boehringer Ingelheim International GmbH or one or more of its affiliated companies

# 4.1.7 Storage conditions

Drug supplies will be kept in their original packaging and in a secure limited access storage area according to the recommended storage conditions on the medication label. The shipping, labelled storage conditions and the available stability data used for assessment in the event of a temperature excursion described in the Stability and Packaging Information (SPI) is reflected in the Mini-tag® profile. The Mini-tag® is validated and is the leading temperature monitoring system used for IMP in this trial. Site staff will be trained on its usage by the time the medication is received at site. For details of storage conditions, please refer to the ISF. A Mini-tag® status site log must be maintained for documentation.

If the storage conditions are found to be outside the specified range, the Clinical Research Associate CRA (as provided in the list of contacts) must be contacted immediately.

For more details, please see the relevant instructions in the ISF.

# 4.1.8 Drug accountability

The investigator or designee will receive the investigational drugs delivered by the sponsor or delegate when the following requirements are fulfilled:

- Availability of a signed and dated clinical trial protocol.
- Approval of the clinical trial protocol by the IRB/ethics committee.
- Availability of a signed and dated clinical trial contract between the sponsor or delegate and the investigational site.
- Approval/notification of the regulatory authority, e.g., competent authority.
- Availability of the *curriculum vitae* of the Principal Investigator.
- Availability of the proof of a medical license for the Principal Investigator (if applicable)
- Availability of FDA Form 1572 (if applicable)

Investigational drugs are not allowed to be used outside the context of this protocol. They must not be forwarded to other investigators or clinics.

The investigator or designee must maintain records of the product's delivery to the trial site, the inventory at the site, the use by each trial participant, and the return to the sponsor or warehouse/drug distribution centre or alternative disposal of unused products. If applicable, the sponsor or warehouse/drug distribution centre will maintain records of the disposal.

These records will include dates, quantities, batch/serial numbers, expiry ('use by') dates, and the unique code numbers assigned to the investigational medicinal product and trial participants. The investigator or designee will maintain records that document adequately that the trial participants were provided the doses specified by the CTP and reconcile all investigational medicinal products received from the sponsor. At the time of return to the sponsor and/or appointed CRO, the investigator or designee must verify that no remaining supplies are in the investigator's possession.

Page 68 of 177

Proprietary confidential information © 2023 Boehringer Ingelheim International GmbH or one or more of its affiliated companies

# 4.2 OTHER TREATMENTS, EMERGENCY PROCEDURES, RESTRICTIONS

#### 4.2.1 Other treatments and emergency procedures

Systemic hypersensitivity including and anaphylactic reaction
In case of systemic hypersensitivity including and anaphylactic reaction emerging during or after of trial medication, the investigator should consider in accordance with severity of the reaction and local standard of care to

- Immediately interrupt the
- Treat with systemic antihistamines, i.v. steroids, and in case of a severe allergic reaction (eg, anaphylactic reaction) epinephrine

Also draw a plasma sample for IgE and ADA as detailed in the Laboratory Manual (ISF). Please initiate the evaluation of histamine, serum tryptase, and complement components.

In case of	based on tri	al participant's clinical
course and medical judgment, the	be re-initiated/the	be
continued in case of mild or moder	ate	(according
to Common Terminology Criteria f	for Adverse Events (CTCAE) g	rading in section of the
ISF) at lower speed with gradual in	crease to complete the	as detailed in
the Instructions for Preparation and	Handling of spesolimab/place	bo in the ISF. In any case,
the total duration of should	d not exceed	Information about the
maximum time between the start of		
trial participant is de	etailed in the Instructions for Ph	narmacist filed on the ISF.

In case of anaphylactic reaction based on the criteria discussed in the statement paper from Sampson HA (Appendix 10.20 [R11-4890]) suspected to be caused by the trial medication, the investigator should permanently discontinue treatment with spesolimab. When a delayed hypersensitivity reaction is suspected, please draw a blood sample for laboratory assessment and evaluate for signs of extra-cutaneous organ involvement. The decision to discontinue treatment and/or restart treatment after resolution of the reaction should be based on reaction type and severity. See Section 3.3.4 for reference.

Severe infections (according to CTCAE grading in Section 15 of the ISF), serious infections, opportunistic or mycobacterium tuberculosis infections

Treatment of the infection should be initiated promptly according to local standard of care. No further trial medication should be administered until the active infection has been resolved. Treatment with spesolimab may be restarted when the trial participant has recovered according to investigator's assessment. See Section 3.3.4 for reference.

#### Malignancies

In case of occurrence of malignant neoplasm other than appropriately treated basal cell carcinoma or squamous cell carcinoma of the skin or in situ carcinoma of uterine cervix, the investigator should discontinue treatment with spesolimab. See Section 3.3.4 for reference. Diagnostics and treatment must be initiated according to local standard of care (SoC).

Page 69 of 177

Proprietary confidential information © 2023 Boehringer Ingelheim International GmbH or one or more of its affiliated companies

# Suicidality

In case a trial participant develops suicidal ideation of type 4 or 5 in the Columbia-Suicide Severity rating Scale (C-SSRS) (i.e. active suicidal thoughts with method and intent but without specific plan, or active suicidal thoughts with method, intent and plan) or any suicidal behaviour (i.e. actual attempt, interrupted attempt, aborted attempt, or preparatory acts or behaviour), the trial participant should immediately be referred to a mental health professional for further work-up and permanently discontinue trial treatment. See Section 3.3.4 for reference.

Overall, the choice of SoC treatment will be left at the discretion of the investigator. The sponsor will not provide/supply SoC treatments to the sites.

Any of the above treatments (including an estimate on dispensed medication), defined in this section, must be documented in the source data and documented in CRF (concomitant medications and AEs) and the corresponding AE report, if applicable.

#### 4.2.2 Restrictions

# 4.2.2.1 Restrictions regarding concomitant treatment

Trial participants must not participate in another investigational drug or device trial or receive other investigational treatment(s) while enrolled in this trial.

The following medications/medication classes are restricted during trial treatment and prior to Visit 2 for durations as specified in Table 4.2.2.1: 1. Please see Section 3.3.4 for withdrawal information regarding the use of restricted medications.

c40061625-02 Clinical Trial Protocol Page 70 of 177

Proprietary confidential information © 2023 Boehringer Ingelheim International GmbH or one or more of its affiliated companies

Table 4.2.2.1: 1 Restricted medications in Part 1 (Phase IIb)\*

Medications/ medication classes	Washout period prior to V2 (baseline)	V2 to V14	From V14 to EoT
Systemic antibiotics 	4 weeks	Restricted for HS except for HS-disease worsening after V6 (definition in Section 4.2.3)	Restricted for HS except for HS-disease worsening after V14
Systemic corticosteroids 	2 weeks	Restricted for HS. For non-HS indications, only short courses are allowed 	Restricted for HS 
Immunosuppressive/ immunomodulatory biologics	12 weeks or 5 half-lives whichever is longer	Restricted for HS and non-HS indications	Restricted for HS and non-HS indications
Other systemic non- biologic immunomodulatory and immunosuppressive agents	4 weeks or 5 half-lives whichever is longer	Restricted for HS and non-HS indications	Restricted for HS and non-HS indications
Live vaccines 	6 weeks	Restricted	Restricted
Opioid analgesics	2 weeks	Restricted for HS and non-HS indications	Restricted for HS 
Spironolactone 	1 week	Restricted for HS and non-HS indications	Restricted for HS
Metformin 	1 week	Restricted for HS and non-HS indications	Restricted for HS
Topical cannabis oil	1 week 	Restricted for HS	Permitted
Systemic medicinal cannabis	3 weeks	Restricted for HS and non-HS indications	Restricted for HS
Topical corticosteroids for HS 	2 weeks	Restricted for HS	Restricted for HS up to Visit 23.
Topical JAK inhibitors	12 weeks	Restricted for HS	Restricted for HS up to Visit 23

\* Restricted medications are expected to be revised and adapted if needed for Part 2 (Phase III)

- 3 Live vaccines are restricted for 16 weeks after the last dose of spesolimab.
- 4 After Visit 14 opioid analgesics other than tramadol are restricted for HS.
- 5 Restricted if used for HS. If used for non-HS indication, dose should be stable for at least 12 weeks prior to V2. Metformin and spironolactone can be initiated for non-HS indications after Visit 14
- 6 Restricted if used over HS-affected areas. Other alternative therapies for HS are restricted, unless permitted after discussion with the investigator and trial team.
- 7 Prior to Visit 23 topical corticosteroids are allowed for non HS indications for areas not concurrently involved by HS.
- 8 Use of immunomodulatory/immunosuppressive biologics other than for HS meets exclusion criterion #2.

 Some conditions apply on the use of systemic antibiotics, please see Section 4.2.3.1.

 Systemic corticosteroids as short courses, i.e. approximately 1- 2 weeks at the discretion of the investigator, can be used for indications other than HS

Clinical Trial Protocol

Page 71 of 177

Proprietary confidential information © 2023 Boehringer Ingelheim International GmbH or one or more of its affiliated companies

#### 4.2.2.2 Restrictions on diet and lifestyle

No specific restrictions on diet or lifestyle of the trial participants are required.

#### 4.2.2.3 Contraception requirements

Throughout the trial, and for a period of at least after last trial drug administration, WOCBP must use highly effective methods of birth control per ICH M3 (R2) that result in a low failure rate of less than 1% per year when used consistently and correctly. A list of contraception methods meeting these criteria is provided in the participant information.

# Female trial participants

Examples of acceptable methods of birth control for this trial:

- Combined (oestrogen and progestogen containing) hormonal birth control that prevents ovulation (oral, intravaginal, transdermal)
- Progestogen-only hormonal birth control that prevents ovulation (oral, injectable, implantable)
- Intrauterine device (IUD) or intrauterine hormone-releasing system (IUS)
- Bilateral tubal occlusion
- Vasectomised sexual partner with documented absence of sperm

OrTrial participants must abstain from male-female sex. This is defined as being in line with the preferred and usual lifestyle of the trial participant. Periodic abstinence (e.g., calendar, ovulation, symptomthermal, post-ovulation methods), declaration of abstinence for the duration of exposure to study drug, and withdrawal are not acceptable.

# Male trial participants

Because of the negative outcome of the completed BI teratogenicity study, a double barrier method of contraception is not required. Contraception of male trial participants and female partners of male trial participants are not required. Systematic collection of pregnancy data in female partners of clinical trial participant is not required [c03320877-11].

#### 4.2.3 Concomitant medications/interventions

The following sections provide definition of certain terms used in this trial and additional information on certain concomitant medications and lesion interventions. The sponsor will not provide/supply these treatments to the sites.

Any medication received by trial participant from Visit 1 should be recorded in the appropriate concomitant medications page in the eCRF.

**Rescue medication** is defined as the treatment for HS disease worsening and includes systemic antibiotics and/or immunosuppressive biologics such as TNF-inhibitors.

**HS Disease worsening** is defined as total AN count is 150% of baseline AN count. For example, for a baseline AN count of 10, disease worsening should be interpreted as an AN count of 15 and above.

Page 72 of 177

Proprietary confidential information © 2023 Boehringer Ingelheim International GmbH or one or more of its affiliated companies

# 4.2.3.1 Antibiotic use during the trial

#### Non-HS use

From randomisation up to Visit 14 systemic antibiotics can be used for indications other than HS for a duration of less than or equal to 4 weeks. The same restriction applies to the period from Visit 14 to Visit 23 with a maximum of 4 consecutive weeks of systemic antibiotics allowed for non-HS indications.

**HS use** (as defined above in Section 4.2.3):

- At or after Visit 6 if the trial participant requires systemic antibiotics for HS disease worsening (as defined above in Section 4.2.3), monotherapy with doxycycline 100 mg orally twice daily-may be used for a maximum period of 2 weeks, and not more than a total of 4 weeks up to Visit 23 After V23, systemic antibiotics can be used for HS disease worsening (duration as per investigator discretion).
- Please refer to the ISF for alternative oral antibiotics allowed in this trial.
- Parenteral antibiotics are restricted for HS until based on roll over status.

Concomitant use of systemic antibiotic therapy for treatment of HS other than the above is not allowed.

# 4.2.3.2 Analgesics use during the trial

Opioid analgesics are restricted for HS and non-HS indications up to Visit 14

After Visit 14 opioid analgesics other than tramadol are restricted for HS. After Visit 14, opioid analgesics can be allowed for non-HS indications as per investigator discretion.

If a trial participant is on a non-opioid analgesic for HS and non-HS indication (e.g. osteoarthritis), the patient may continue the analgesic, provided the dose is stable for 14 days prior to Baseline and it is anticipated to remain stable throughout the study.

If a trial participant's pain (HS-related or non-HS-related) worsens after Baseline, they may initiate or increase the non-opioid analgesic therapy.

Use of analgesics will be documented in the Patient Diary and the CRF.

#### 4.2.3.3 Lesion intervention

In the event that an acutely painful lesion occurs that requires immediate intervention, physicians will have the option to perform protocol-allowed interventions.

Only two types of interventions are allowed in this trial: intra-lesional steroid and Incision and Drainage (I&D).

• If I&D is performed, only over the counter antiseptic wash can be used. Concomitant medications associated with the lesion intervention must be captured in the medical records.

[figure not shown]
Page 73 of 177 Proprietary confidential information © 2023 Boehringer Ingelheim International GmbH or one or more of its affiliated companies

Intralesional steroid injections of triamcinolone up to can be used for a single lesion at one time.

Up to Visit 14 a total of two protocol-allowed interventions are permissible. After Visit 14 up to Visit 23 a total of two protocol-allowed interventions are permissible. For each period, an intervention can maximally occur on two different lesions at the same time or on the same lesion at two different study visits. From Visit 23 to EoT, there are no restriction in the number of lesion interventions.

Lesions that have been subjected to intervention should not be counted in future assessments.

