# Part 1 (Phase IIb)

# **Efficacy**

Lesion counts clinical endpoints

- Percent change from baseline in dT count at each scheduled assessment.
- Achievement of at least 50% reduction from baseline in dT count at each scheduled assessment.
- Occurrence of complete elimination of dT at each scheduled assessment.
- Time to first occurrence of complete elimination of dT during the treatment period.
- Percent change from baseline in abscess count at each scheduled assessment.
- Achievement of at least 50% reduction from baseline in abscess count at each scheduled assessment.
- Occurrence of complete elimination of abscess at each scheduled assessment.
- Percent change from baseline in total AdT count at each scheduled assessment.
- Achievement of at least 50% reduction from baseline in AdT count at each scheduled assessment.
- Percent change from baseline in inflammatory nodule (N) count at each scheduled assessment.
- Percent change from baseline in total ANdT count at each scheduled assessment.
- Achievement of at least 50% reduction from baseline in ANdT count at each scheduled assessment.

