A non-flat dose response is established if at least one dose response pattern is statistically significant, rejecting the null hypothesis of a flat dose response relationship over percent change from baseline in dT count at jointly for each of the candidate dose response models with a contrast test controlled for the family-wise type I error rate at 1-sided  $\alpha$  of 0.05.

If non-flat dose-response is established, the statistically significant (best fitting) model(s) from the above candidate set are refitted to the data to generate new estimates for all model parameters. If more than one model is significant, the weighted average model will be evaluated to identify the for Part 2 for Pa

In addition to the results from \_\_\_\_\_\_ a beneficial treatment effect relative to placebo will be evaluated.

Baseline is defined as the last available data collected at Visit 2 prior to administration of first dose of study medication, or last available screening data if Visit 2 data are missing.

Page 110 of 177

Proprietary confidential information © 2023 Boehringer Ingelheim International GmbH or one or more of its affiliated companies

The primary analysis will be performed using the TS, as defined in Section 7.2.1. All available data from the TS in each active treatment arm and the placebo arm up to Week 8 will be used. Trial participants will be analysed according to the stratum to which they belong (regardless of any mis-assignment to treatment based on identification of the wrong stratum), as such an error occurs before randomisation and is therefore consistent with regulatory guidance.

In the primary analysis intercurrent events are handled with treatment policy approach, except for death (unexpected), see Section 7.2.2.

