# 10.4 INTERNATIONAL HIDRADENITIS SUPPURATIVA SEVERITY SCORE SYSTEM (IHS4)

International Hidradenitis Suppurativa Severity Score System (IHS4). A nodule (inflammatory nodule) is a raised, three-dimensional, round, infiltrated lesion with a diameter of >10 mm. An abscess is a tender but fluctuating mass with a diameter of >10 mm, surrounded by an erythematous area; the middle of an abscess contains pus. A draining tunnel is a raised, tender but fluctuating longitudinal mass of variable length and depth, ending at the skin surface, and sometimes oozing a fluid. Fistulae and sinuses are examples of tunnels.

*Fig. source*: [R20-3045].

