6.7 BASELINE, TIME WINDOWS AND CALCULATED VISITS

Unless otherwise specified, measurements reported with date and time and taken prior to start of administration of trial treatment will be considered pre-treatment values; measurements reported with a date only (and no time) and taken on the day of first administration of trial treatment will also be considered pre-treatment values. These pre-treatment values will be assigned to visits according to the nominal visit number as recorded on the eCRF or as provided by the laboratory.

Patient reported output (PRO) measurements reported prior to/on the date of the drug administration will be taken as pre-treatment values, regardless the time of measurements taken if there exist.

Baseline, unless otherwise specified, is defined as the last measurement collected prior to the start of administration of the trial treatment.

Measurements taken after start of administration of trial treatment will be considered either on- or off-treatment values based on the definition in Section 6.1, and will be assigned to visits for statistical analysis, if applicable, as defined below.

[figure not shown]
Analysis of AE data, potentially clinically significant abnormal laboratory values, concomitant medication or non-drug therapies, as well as use of rescue medication will not be based on visits. Frequency tables for these data will be using on-treatment data and categorized based on their occurring/starting dates. Therefore, no assignment to time windows will be necessary for such data.

The derivation of the last value, minimum value and maximum value of laboratory and vital signs data will consider all on-treatment values (whether or not selected in any time window; see Table 6.1: 1 for definition of the on-treatment period) within the period of interest; these will be derived for analysis of laboratory and vital signs data.

All other safety, efficacy and biomarker measurements will be assigned to visits based on extended time windows around the planned visit dates, defined relative to the day of first trial treatment (which is scheduled for Visit 2). These extended time windows are defined in Table 6.7: 1 and Table 6.7: 2.

c43421787-01

c43421787-01

c43421787-01

Proprietary confidential information © 2024 Boehringer Ingelheim International GmbH or one or more of its affiliated companies.

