7.4 PRIMARY OBJECTIVE ANALYSIS

7.4.1 Main analysis

Part 1 (Phase IIb)

Date: 07-08-2024, Version 1.0

The main analysis of the primary endpoint will use a treatment policy estimand. Details of handling the intercurrent events are addressed in Section 7.2.2 of the clinical trial protocol and Table 6.3.1. This main analysis of the primary efficacy endpoint will be performed on the full analysis set. Subjects will be analyzed according to the stratum to which they actually belong. Missing data will be handled using a mixed effects model with repeated measures (MMRM) under the assumption of missing at random.

The descriptions below are based on the primary objective and secondary objective, respectively.

Proprietary confidential information © 2024 Boehringer Ingelheim International GmbH or one or more of its affiliated companies.

Primary Objective: Dose Finding

For the primary endpoint analysis, first a mixed effect model for repeated measurements (MMRM) is calculated to estimate the treatment effects and the corresponding covariance matrix. Using the MCPMod approach (9.4, 9.5), these estimates are then further used to

- (1) test for a non-flat dose response curve
- (2) identify suitable dose-response shapes out of a selection of candidate models.

The final dose-response model is derived as a weighted average over all significant model shapes. Planned total dose before Week 8 will be used to evaluate dose response curve.

Details on both the specification of the MMRM and the MCPMod approach are given in the CTP Section 7.2.2.

MMRM analysis

The % change in dT count from baseline (Visit 2), at Visits 4, 6, 8 and 10 (, 8) will be evaluated using an MMRM accounting for the following sources of variation: fixed, categorical effects of treatment at each visit, TNFi status at baseline and categorical baseline dT count at each visit. The unstructured covariance structure will be used to model the within patient measurements. To estimate denominator degrees of freedom the Kenward-Roger approximation will be used.

SAS code for MMRM for the endpoint of dT count:

PROC MIXED DATA=alldat cl method=reml;

CLASS dt_base_categorical visit trt TNFi subject;

MODEL ept = TNFi visit*trt dt_base_categorical *visit/ddfm=kr s CL;

REPEATED visit / subject= subject type=un r rcorr;

LSMEANS visit*trt / pdiff=all om cl alpha=0.05 slice=visit;

RUN;

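### Treated lesions drop out of later counts while baseline stays fixed, so a treated baseline tunnel that still drains scores as resolved in the primary dT endpoint

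*Protocol*

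**What the plan says.** Protocol 4.2.3.3 allows intralesional steroid or incision and drainage "In the event that an acutely painful lesion occurs that requires immediate intervention". It caps use: "Up to Visit 14 a total of two protocol-allowed interventions are permissible". It then gives the counting rule: "Lesions that have been subjected to intervention should not be counted in future assessments". The rule has no time limit and names no lesion type.

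Baseline is fixed. Protocol 7.2.3 (Part 1): "Baseline is defined as the last available data collected at Visit 2 prior to administration of first dose of study medication", with screening data as fallback. SAP 6.7: "Baseline, unless otherwise specified, is defined as the last measurement collected prior to the start of administration of the trial treatment".

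The Part 1 primary endpoint is percent change in dT count at Week 8 (SAP 5.1). SAP 7.4.1 analyses it by MMRM: "The % change in dT count from baseline (Visit 2), at Visits 4, 6, 8 and 10". Visit 10 is Week 8 and falls inside the window up to Visit 14 in which interventions are allowed.

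Lesion intervention is not named in the rescue definition (Protocol 4.2.3) or in the intercurrent events listed in Protocol 7.2.2 and SAP 6.3. SAP 7.2 does mention non-drug rescue therapy. Protocol 7.2.2 leaves unlisted events to blinded review, with the strategy to be documented in the TSAP.

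**The concern.** The exclusion may be meant to keep the effect of the procedure out of the drug effect. With a fixed baseline it does something else: a treated baseline lesion is scored as absent at every later visit, even if the procedure failed. For a draining tunnel, that is an improvement in the primary variable.

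Nothing in the text keeps tunnels outside the rule. Appendix 10.4 describes them in terms compatible with an acutely painful lesion: "A draining tunnel is a raised, tender but fluctuating longitudinal mass of variable length and depth".

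The lowered count enters the treatment-policy MMRM unchanged. IHS4 is derived from the same lesion counts, so it is lowered too. Part 1 testing is non-confirmatory (Protocol 7.1), but the Week 8 dT result informs the choice of dose and whether Part 2 proceeds (Protocol 2.1.1). A 50% dT reduction is also a potential Part 2 key secondary endpoint (Protocol 2.1.3).

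**Working it through.** The legible plan gives no figure to reproduce for this point, so the check applies the endpoint's own arithmetic.

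**Inputs**
- k = number of baseline tunnels treated, still draining and left out of the count (Protocol 4.2.3.3).
- b = baseline dT count. The entry threshold (inclusion criterion 8) is not legible, so b = 1 to 5 is an assumed range.
- True count unchanged, so the recorded count is b − k.
- Assumed maximum effect in Part 1: 30 percentage points versus placebo (Protocol 7.2.3).

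**Step 1: one participant.** Recorded change = 100 × ((b − k) − b) / b = −100k/b. The true change is 0.

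| b | k = 1 | k = 2 |
|---|---|---|
| 1 | −100% | not possible |
| 2 | −50% | −100% |
| 3 | −33.3% | −66.7% |
| 4 | −25% | −50% |
| 5 | −20% | −40% |

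**Step 2: responder endpoints.** Protocol 2.2.2 lists "Achievement of at least 50% reduction from baseline in dT count at each scheduled assessment". With k = 1 it is met when 1/b ≥ 0.5, so at b = 1 or 2. Complete elimination of dT is met at b = 1.

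**Step 3: how reachable k = 2 is.** Section 4.2.3.3 limits each period to two different lesions treated at the same time, or one lesion treated at two visits. It also limits intralesional steroid to one lesion at a time. Read literally, k = 2 needs two baseline tunnels treated together, at least one by incision and drainage. Two treatments of one lesion give k = 1. The k = 2 column is a corner case.

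**Step 4: arm means, k = 1.** Shift in the mean difference = (difference between arms in the share affected) × 100/b, taking b as the same for everyone.
- A 1-point shift needs a difference of b percentage points: 2 to 5 at b = 2 to 5.
- A 3-point shift (10% of 30) needs 3b: 6, 9, 12 or 15 percentage points at b = 2, 3, 4 or 5.
- Equal shares and baseline counts give 0.
- Direction, with assumed shares of 20% and 5% at b = 2: 0.15 × 50 = 7.5 points. If placebo has the larger share, a 30-point effect reads 22.5. If the active arm has it, the effect reads 37.5.

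**Step 5: does adding back repair it?** Counting the treated tunnel as present gives 100 × (b − b)/b = 0%, the true value, at every b. Removing it from both baseline and follow-up also gives 0% while an untreated tunnel remains, but gives 0/0 when every baseline tunnel was treated. Adding back is the safer form.

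**The case against.** The strongest reply is that the event is only possible. The trigger speaks of a painful lesion that occurs, which most naturally means a new acute lesion. The problem needs a tunnel counted at baseline, treated before Visit 10 and still draining. The documents give no rate for this and no imbalance between arms. That stands. A reader might infer that the primary result is biased, or biased towards spesolimab; the documents support neither.

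A reader might also infer a breach of the treatment-policy strategy. That goes too far. Protocol 7.2.2 and SAP 6.3 use the value of the variable as defined, and a count made under 4.2.3.3 is consistent with them. The weakness lies in how the variable is defined.

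Parts of the SAP are blacked out, including text after 5.2.2, Section 6.5, parts of 7.4 and Section 10. A derivation rule could be there, so the point cannot be read as saying that the plan has none.

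HiSCR, flare and rescue status are reached too, but in Part 1 only through exploratory binary endpoints, and HiSCR and flare only near their thresholds. Treatment summaries by arm (SAP 7.2) partly cover use, but no legible text plans them by lesion type.

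Finally, moving the main count to lesions as seen partway through Part 1 would mix two definitions of the primary variable. That is right, and the fix allows for it.

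What remains is that the sentence, as written, assigns a wrong value whenever the event happens.

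**Conclusion.** The concern holds as a flaw in the counting rule. A treated baseline tunnel that still drains is scored as resolved, worth 100/b points per participant: 50, 33, 25 or 20 at an assumed b of 2 to 5. One such tunnel meets the 50% dT endpoint at b = 1 or 2, and complete elimination at b = 1. The two-tunnel figures should not be read as typical.

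At arm level no size can be stated. A 3-point shift would need a 6 to 15 percentage-point imbalance at b = 2 to 5. The direction follows whichever arm has more such exclusions: towards the null if placebo, in favour of spesolimab if active.

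This rests on the literal reading of 4.2.3.3, on tunnels falling within the word lesion, and on the legible text only. Confidence is medium. It should be fixed, because the correction is small and the Part 2 text is still to be amended.

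**What to change.** **Part 1.** Keep the main counting rule. Flag each treated lesion with its type, intervention, date and whether it was counted at baseline, and tabulate by arm. Add a sensitivity analysis of the Week 8 and Week 16 dT and IHS4 endpoints that adds each treated lesion back as present from the intervention date to Visit 14.

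**Part 2 amendment.** Replace the exclusion sentence with wording such as: *Treated lesions continue to be assessed, recorded and flagged at each visit, and are not scored as absent merely because they were treated.* Run the carried-as-present analysis alongside.

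**SAP 6.3.** List lesion intervention with its strategy, and state whether it is rescue for the binary endpoints. If it is, the composite strategy makes the participant a non-responder. If it is not, the lowered count can make the same participant a responder.

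If a blacked-out SAP section already has a rule, reconcile it with 4.2.3.3.

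**Cost.** One CRF flag, one SAP row, one sensitivity analysis, one table and one protocol sentence. Assessors must already identify treated lesions in order to omit them. Carrying lesions as present is conservative where the intervention truly cleared them, and an as-seen count in Part 2 includes any effect of the procedure; the two should be read together. Part 1 visits already counted cannot be recounted, but the flag shows which values are affected. No change is proposed to which interventions are allowed.
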